### Time Frame

These analyses include resident and staff data from January 1, 2021 - July 31, 2021. Data was collected across six time points:

- Baseline: 1/1/2021 – 3/31/2021
- 3-month follow-up: 4/1/2021 – 6/30/2021
- 6-month follow-up: 7/1/2021 – 9/30/2021

- 9-month follow-up: 10/1/2021 – 12/31/2021
- 12-month follow-up: 1/1/2022 – 3/31/2022
- 15-month follow-up: 4/1/2022 – 7/30/2022

## Data Collection and Sources

Person-level (individual health worker and resident) measures were collected at baseline, 3-, 6-, 9-, 12-, and 15-months post-baseline. These limited datasets included information from routinely collected administrative data at each participating agency, such as dates of COVID-19 events for staff and residents (i.e., dates of positive test results, hospitalizations, deaths, and vaccinations). We also received the unique, encrypted identifiers of the group home(s) that residents lived in and staff worked in during each 3-month data collection period. We also obtained information on demographic characteristics (e.g., age, gender, race/ethnicity) for residents and staff. All data were transmitted from the provider organizations to Massachusetts General Hospital using a secure e-mail portal.

## Analytical and Statistical Approaches

The raw incidence rates were summarized across the homes by treatment group (Tailored Best Practices TBP vs Generic Best Practices GBP) for each time period. To compare the effectiveness between these groups, we fit a Poisson generalized linear mixed model with log-link for the group home level infection incidence rates over the 5 follow-up periods. The model included main effects for treatment group, linear and quadratic time trends over the follow-up periods, and interaction effects between treatment and the time periods. The model additionally included fixed effects for randomization factors, baseline incidence at each home, and group home agency, along with a group-home level random intercept.

A joint Wald test was performed to assess whether there were significant differences in the trends between treatment groups based on this model for the main effect for treatment including interactions between treatment and time trends. Estimates of the conditional incidence rate ratio (IRR) at each time point were calculated based on the linear combination of

the treatment main effect and treatment by time interaction effects. Correction for type I error was controlled by Bonferroni's method. Marginal mean incidence rates by treatment group per 100 person-months were estimated based on the model assuming 0 random effect. These analyses were repeated for various subgroups: staff, residents, IDD residents, and SMI residents separately. The analyses were performed in Stata 16.

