Persons with SMI and ID/DD are disproportionately vulnerable to COVID-19 for three reasons: **(1) Medical vulnerability.** Smoking, chronic obstructive pulmonary disease, cardiovascular disease, and diabetes all increase COVID-19 mortality and are about 2–3 times more prevalent among persons with SMI. People with ID/DD suffer higher rates of COVID-19 risk factors, including pre-existing chronic conditions, heart defects, obesity, chronic respiratory problems or lung disease, lower immune function, cancer, and diabetes. **(2) Residential vulnerability.** The congregate care settings in which many people with SMI and ID/DD live carry many of the same higher risks of COVID-19 transmission currently affecting assisted-living settings and nursing homes across the nation. **(3) Health behavior vulnerability.** Some people with SMI and ID/DD have cognitive, behavioral, and physical challenges that heighten COVID-19 risk by hampering personal protective practices (PPP) (i.e., hand hygiene, physical distancing, use of face masks). Moreover, the staff who work in congregate care settings are often subject to high rates of exposure, have low socioeconomic status, use public transportation, and lack personal protective equipment. This collection of factors contributes to an extraordinarily high risk of COVID-19 morbidity, and mortality. **Despite payment reforms and mandated best practices for COVID-19 for congregate care by the MA Department of Public Health, rates of coronavirus illness for residents with SMI and ID/DD are 8 times higher (12%), and for staff 2 times higher (3.0%), compared to the general population in the surrounding “hot spot” communities (1.5%) selected for this study.** *This tragic health disparity confirms that we lack the knowledge of how to optimally tailor best practices for this highly vulnerable population and the staff who provide their care to effectively reduce their high risk of COVID-19 and COVID-19 related mortality.* We do not know (1) optimal practical screening practices for people with SMI and ID/DD, (2) how to feasibly and effectively provide isolation in the close shared quarters of group homes, (3) how to conduct reliable contact tracing for staff and residents, or (4) how to support pragmatic and effective personal protective practices. The proposed study will produce actionable results addressing these knowledge gaps that can be immediately implemented within the first few months of the project.

RESEARCH DESIGN AND METHODS

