### Sample Size Calculations and Power

For power calculations we assumed a 2-tailed test with significance level .05, intraclass correlation (ICC) of 0.02 within the four randomization clusters (i.e., highest and lowest prevalence GHs within GBP and TBP), and ICC of 0.50 for repeated measures at the GH-level. Given COVID-19 incidence as of May 2020 rates based on available COVID-19 prevalence data for GHs residents and staff, we will have at least 80% power to detect 8.7 and 6.3% percentage point difference of COVID-19 infection between GBP and TBP for residents (ID/DD combined) and staff, respectively. We used conservative assumptions, given the possibility of undetected COVID-19 in GHs. The primary outcome is COVID-infections in both staff and residents with correction for type I error applying Bonferroni's method.

**Table 1.** Power calculations.

	Estimated COVID-19 Prevalence		Difference	Cohen's d a	Power
Population	Control (GBP)	Intervention (TBP)			
Group Home Staff	13.10%	6.80%	6.30%	0.38	80%
Residents with SMI & ID/DD combined	26.50%	17.80%	8.70%	0.28	80%
Residents with ID/DD	40%	30%	10%	0.24	80%
Residents with SMI	13.10%	6.80%	6.30%	0.38	80%

aSmall effect=0.2; Medium effect=0.5

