### [Changes to the Original Study Protocol](#)

We used an ANCOVA model in which outcomes observed at baseline were adjusted for as a covariate rather than included as a follow-up time point because of discrepancies in the definition of the fidelity score between the baseline and follow-up time points (resident masking was removed after baseline due to policy change). This approach was adopted for other endpoints to maintain consistency across all primary analyses. A quadratic term for time was included in the model to improve the model fit in accordance to observed trends.

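### The co-primary infection model has no allowance for overdispersion within a home and period, so the joint Wald test rejects too often if cases come in outbreaks

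*SAP*

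**What the plan says.** In the SAP's analysis section for the effectiveness co-primary, the model is described thus: "we fit a Poisson generalized linear mixed model with log-link for the group home level infection incidence rates over the 5 follow-up periods". On fixed effects: "The model included main effects for treatment group, linear and quadratic time trends over the follow-up periods", together with treatment-by-time interactions, randomization factors, baseline incidence and agency. The single random term is added in the words "along with a group-home level random intercept".

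The test follows: "A joint Wald test was performed to assess whether there were significant differences in the trends between treatment groups based on this model". It covers the treatment main effect and its interactions with time, which is 3 degrees of freedom. For single periods: "Estimates of the conditional incidence rate ratio (IRR) at each time point were calculated", from the same coefficients. Type I error is handled by Bonferroni; the number of tests is not stated.

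The section on changes to the protocol shows that fit was examined for the time trend: "A quadratic term for time was included in the model to improve the model fit in accordance to observed trends". It does not mention dispersion. Neither the SAP text available nor the protocol names a negative binomial model, a home-by-period random effect, a scale parameter or a robust variance. The opening part of the SAP, before the effectiveness outcome, was not available to check.

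**The concern.** A home intercept absorbs differences between homes that last through all five periods. It does not absorb a home having several cases in one quarter and none in the next. The documents give reason to expect that pattern: the protocol's background section describes raised transmission risk in congregate care and close shared quarters, and isolation and contact tracing are among the targeted practices.

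Treatment by linear time and treatment by quadratic time are within-home contrasts. Under this model their standard errors rest on Poisson variance alone, so they are too small if counts are overdispersed within homes.

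The joint test carries the co-primary effectiveness comparison, and the trial is meant to inform whether TBP merits system-wide dissemination. The test could report a difference between arms in time pattern, or in particular periods, that is only outbreak noise. Bonferroni does not repair this, because the single test already exceeds its own nominal level.

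**Working it through.** **The plan's own figure.** The SAP's 80% power is approximately reproduced with the home as unit, 200 per arm, two-sided 0.05, six waves and "ICC of 0.50 for repeated measures at the GH-level". The variance factor is (1 + 5 × 0.50)/6 = 0.583, so the effective n is 200/0.583 = 343 per arm. Power is 78.5% for 26.5% vs 17.8% (residents) and 78.8% for 13.1% vs 6.8% (staff). This is a prevalence calculation and contains no assumption about dispersion of counts.

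**Inputs.**
- Homes: 200 per arm, 5 follow-up periods (protocol design section; SAP).
- People per home: 2200/400 = 5.5 residents and 3300/400 = 8.25 staff (protocol).
- Mean count from SAP Table 1 control rates: (5.5 × 0.265 + 8.25 × 0.131)/5 = 2.54/5 = 0.51 per home-period.
- Lower mean from the protocol's background rates: (5.5 × 0.12 + 8.25 × 0.03)/5 = 0.91/5 = 0.18.
- Assumption: these prevalences are read as cumulative 15-month incidence.
- Dispersion D, the within-home variance-to-mean ratio, is not in the documents and is varied. If outbreaks of k cases arrive at random, D = E[k²]/E[k]. Sizes 1 or 2 (80/20%) give 1.6/1.2 = 1.33. Sizes 1, 2, 3 (50/30/20%) give 3.5/1.7 = 2.06.

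**Closed-form check.** With time centred, suppose the main effect is correctly scaled and the two interaction terms have their Wald contributions inflated by D. The joint statistic is then approximately χ²(1) + D·χ²(2), compared with 7.815 (5%) or 9.348 (2.5%). Since D·χ²(2) is exponential with mean 2D, the rejection probability at critical value c is P(χ²(1) > c) + E[exp(−(c − χ²(1))/(2D)); χ²(1) < c].

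**Null simulation.** No treatment effect, mean 0.5, lognormal home effect with variance 0.5, negative binomial counts within home. The fitted model was the SAP's Poisson random-intercept model with baseline incidence, three binary strata and six agencies; follow-up was equal in all homes. There were 4000 replicates per D. The 2.5% level assumes Bonferroni over two co-primaries.

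| D | Joint, nominal 5%: closed form | Joint, nominal 5%: simulated | Joint, nominal 2.5%: closed form | Joint, nominal 2.5%: simulated | Period IRR 95% intervals excluding 1 |
|---|---|---|---|---|---|
| 1 | 5.0% | 5.2% | 2.5% | 2.5% | 5.2–5.7% |
| 1.25 | 8.3% | 7.9% | 4.6% | 4.6% | 6.1–7.0% |
| 1.5 | 12.0% | 11.7% | 7.3% | 6.9% | 6.4–8.7% |
| 2 | 19.6% | 19.8% | 13.5% | 13.1% | 7.4–11.0% |
| 3 | 33.1% | 33.2% | 25.7% | 26.0% | 9.1–15.1% |

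The treatment main effect (time centred) rejects in 5.3–5.8% throughout. With home-clustered robust variance the joint test rejects in 5.0–6.0% at nominal 5% and 2.7–3.1% at nominal 2.5%; the period IRRs give 5.0–5.8%.

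**Sensitivity.**
- Mean 0.18: joint test 5.4%, 8.1%, 12.8%, 19.1%, 34.1% over the same D values (robust 5.5–7.7%).
- Home variance ln(1 + 0.5/0.25) = 1.1: 6.3%, 12.3%, 19.6%, 33.2% at D = 1, 1.5, 2, 3 (robust 4.9–6.9%). This gives a count ICC of 0.50 at D = 1 only. In general the ICC is 1/(1 + D), so it is 0.40, 0.33 and 0.25 in the other cases.
- Separate code, unequal home sizes, home intercept SD 0.5, agency, strata and baseline left out, 400 replicates: 4.5%, 9.2%, 14.7%, 23.7% at D of about 1, 1.25, 1.5, 2. If each introduction adds on average 0.5 or 1 further case, 16.5% and 26.0%. Robust variance gives 4.3–7.2% and a negative binomial mixed model 4.5–6.0%.
- A further 600-replicate run: 3.8%, 9.3%, 9.3%, 19.8% at D = 1, 1.25, 1.5, 2 (robust 3.5–5.5%; main effect 4.2–5.7%).

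**The case against.** The strongest reply is that the defect is conditional and its size is not in the documents. At D = 1 the joint test is valid. The D values are chosen, and D = 3 exceeds both worked outbreak mixes. That stands: the percentages are a range, and D = 3 is an upper end, not an expectation.

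A second reply is that the SAP does not say how standard errors were computed, so robust variance may have been used. It may have been. But a Poisson mixed model described without any such option reads as model-based, and a plan should state the choice.

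Third, the mean of 0.5 rests on May 2020 rates spread evenly over later periods. The result hardly moves at 0.18, so little turns on this.

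Fourth, robust variance is not a complete cure. In a run with a wave-shaped time profile and simpler quadrature, its error reached about 12% in the heaviest-outbreak cases. Staff cases are also counted in every home worked in, which creates dependence between homes that clustering by home does not remove; this was not simulated. These points stand, and they are why the dispersion estimate and a second model should accompany the robust variance.

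Finally, the scope is narrow: the average effect is nearly protected and single-period inflation is moderate. That is correct, although the protection was shown with time centred, which the SAP does not state.

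**Conclusion.** The concern holds, conditionally. Followed as written, the model leaves the joint Wald test and the period-specific IRR intervals anti-conservative whenever counts are overdispersed within homes. For D between 1.25 and 2 the joint test's error is about 8–20% at nominal 5% (about 5–13% at nominal 2.5%), and single-period errors are about 6–11%. The average treatment effect is essentially unaffected.

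The closed form and the separately coded simulations agree on direction and approximate size. What is uncertain is the trial's actual dispersion, which the documents do not report. Confidence is therefore medium. This should be fixed, but it does not by itself invalidate the comparison.

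**What to change.** - Keep the Poisson mixed model and use home-clustered robust variance for the joint Wald test and all period-specific IRR intervals, in the combined analysis and in the staff and resident repeats.
- Report the fitted within-home dispersion for each analysis.
- Give a negative binomial mixed model as a sensitivity analysis.

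This takes one variance option and one extra model on data already held. The price is width: in the simulation, the log-IRR intervals for the first and last periods are 1.06, 1.12, 1.21 and 1.33 times as wide at D = 1.25, 1.5, 2 and 3, and unchanged at D = 1. The interval for the average effect is essentially unchanged (ratio 0.99–1.00). If the dispersion proves to be near 1, the results will hardly change.

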### [Changes to the Original Study Protocol](#)

We used an ANCOVA model in which outcomes observed at baseline were adjusted for as a covariate rather than included as a follow-up time point because of discrepancies in the definition of the fidelity score between the baseline and follow-up time points (resident masking was removed after baseline due to policy change). This approach was adopted for other endpoints to maintain consistency across all primary analyses. A quadratic term for time was included in the model to improve the model fit in accordance to observed trends.

## Co-Primary Outcome: Implementation

### Outcomes

Fidelity to COVID-19 prevention practices among residents and staff (masking, screening, handwashing, vaccinations, booster vaccinations).

### Covariates

- *Study arm*: General Best Practice (GBP) or Tailored Best Practice (TBP)
- *Agency*: Unique identifier of the six provider organizations.
- *Baseline Fidelity score*: Fidelity scores were calculated by home at baseline.
- *Group Home*: Unique identifier of the group home where resident lived or staff worked.
- *Stratification factors*: Stratification factors used for randomization, derived from the baseline racial and ethnic composition of group home residents and staff and a COVID-19 infection risk score.

### Sample Size Calculations and Power

For power calculations we assumed a 2-tailed test with significance level .05, intraclass correlation (ICC) of 0.02 within the four randomization clusters (i.e., highest and lowest prevalence GHs within GBP and TBP), and ICC of 0.50 for repeated measures at the GH-level.

For the primary implementation outcome, the continuous Best Practices Fidelity score, we will have 80% power to detect minimum 0.21 standardized mean difference between intervention and control (Cohen's  $d = 0.21$ ). For a dichotomous fidelity threshold of 80% Best Practices Fidelity, we will have 80% power to detect 7.2% difference (Cohen's  $d = 0.33$ ).

### Time Frame

These analyses included home-level Program Director (PD) responses to 6 waves of Fidelity surveys distributed between May 1, 2021 - October 31, 2022. Measures were collected during the following time periods:

- Baseline: 5/1/2021 – 7/31/2021
- 3-month follow-up: 8/1/2021 – 10/31/2021
- 6-month follow-up: 11/1/2021 – 1/31/2021
- 9-month follow-up: 2/1/2022 – 4/30/2022
- 12-month follow-up: 5/1/2022 – 7/31/2022
- 15-month follow-up: 8/1/2022 – 10/31/2022

### [Data Collection and Sources](#)

PDs at study sites were completed a brief 10-minute COVID survey covering prevention practices used in the prior 3 weeks. Responses were assessed at baseline, 3-, 6-, 9-, 12-, and 15-months. The survey items were designed in collaboration with care staff and other stakeholders to support the relevance, feasibility, and comprehension of the measures in the routine care context. Surveys were filled out by PDs on a secure web application (REDCap). PDs who completed the survey received \$10 gift cards.

### [Analytical and Statistical Approaches](#)

**Fidelity measures:** Fidelity measures were determined by state level policies in place while the survey was in the field. Since COVID-19 prevention practice policies changed throughout the study period, our definition of Fidelity is dynamic, shifting across time points. The following measures were counted for each time point:

**Table 2.** Relevant Fidelity measures by wave, based on current COVID-19 policies.

	Vaccinations		Boosters		Screening		Hand Washing		Masking	
Time	Residents	Staff								
Baseline										
3-month follow-up										
6-month follow-up										
9-month follow-up										
12-month follow-up										
15-month follow-up										

We followed methodology for developing fidelity scales for evidence-based practices described by Bond and colleagues in preparing the TBP and GBP fidelity scales. We operationally defined 2-4 items assessing each measure, with items scored on a 5- to 6-point continuum with a rating of 5 or 6 indicating full adherence to the fidelity standard and 1 indicating complete lack of adherence. Responses were only included in the analysis if all items were completed. If a home contributed 2 PD responses in one time period, then the responses were averaged.

#### [Changes to the Original Study Protocol](#)

We used an ANCOVA model for the same reasons stated earlier. Quadratic time was added to the model due to observed trends in the data and conditional IRR estimates were generated.
